#### 5.5.4 Treatment Exposure and Compliance

Study drug (Darolutamide / Enzalutamide) exposure and compliance will be summarized using descriptive statistics. The summary of treatment exposure will include number of cycles, duration of treatment, total actual dose and total intended dose. Duration of Exposure is defined as the duration between the first and last dose of treatment (last dose date - first dose date+1). Total Actual Dose is defined as the sum of all treatment administered over the entire course of the study. Total Intended Dose is defined as the sum of intended doses during the duration of exposure, based on no modifications to dose or schedule. Percent Compliance is defined as the Total Actual Dose divided by Total Intended Dose multiplied by 100% for each patient. The frequency and percentage of patients receiving <100%, 100%, and >100% of their dose compliance are summarized.

The number of patients with dose reductions, increased, interrupted and withdrawn (along with their reasons) are all summarized using frequency counts and percentages, for patients that received darolutamide or enzalutamide.

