6.4 Study Intervention Compliance

Participant compliance with study intervention will be assessed at each visit. Compliance will be assessed by direct questioning, counting returned tablets/capsules, etc. The participant should be asked about the reason for obvious non-compliance. Deviation(s) from the prescribed dosage regimen should be recorded in the source records and eCRF.

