6.6.2 Dose modifications

Doses of study intervention may be interrupted or reduced in case of clinically significant toxicities that are related to study treatment. All dose modifications regardless of relatedness should be recorded on the CRF.

Study intervention may be interrupted for situations other than treatment-related AEs such as medical/surgical events or logistical reasons not related to study therapy. Participants should be placed back on study intervention within 28 days of the interruption, unless otherwise discussed with the sponsor. The reason for interruption should be documented in the participant's study record.

Darolutamide

A participant who experiences a darolutamide treatment-related grade 3 or 4 AE should interrupt study treatment until the AE improves to grade 2 or less. Darolutamide treatment is then to be restarted at 300 mg bid.

Additional details are provided in Table 6-1.

Table 6–1 Dose Interruption and/or Reduction for Toxicities Considered Related to Darolutamide Treatment

Severity grade (NCI-CTCAE v 5.0)	Dose modifications	Permanent discontinuation of darolutamide
Grade 0-2	Treat on time. Per investigator's decision to interrupt or reduce darolutamide ^{a,b}	-
Grade 3 or 4	Interrupt until grade ≤ 2 ^a When the severity is grade ≤ 2 , restart at a reduced dose of 300 mg bid ^{b,c}	If the dosing of the study intervention is temporarily or permanently reduced to 300 mg bid and a grade 3 or higher treatment-related AE occurs while the participant is on a dose of 300 mg bid, the participant must be withdrawn from treatment with darolutamide.

Excludes clinically non-significant and asymptomatic laboratory abnormalities

AE = adverse event; bid = twice daily; NCI-CTCAE v 5.0 = National Cancer Institute - Common Terminology Criteria for Adverse Events version 5.0

- a If darolutamide is interrupted for 28 consecutive days, darolutamide should be permanently discontinued.
- b When the AE improves or is resolved, dose escalation to 600 mg bid may be considered at the discretion of the investigator.
- c If the dose is re-escalated to 600 mg and any treatment-related AE with a severity grade 3 or higher occurs, a permanent dose reduction is required. A third occurrence of a grade 3 or higher treatment-related AE requires permanent discontinuation of darolutamide.

Enzalutamide

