Dose modification and/or interruption for toxicities considered related to enzalutamide treatment can be made according to the prescription information ([XTANDI™ Prescribing information](#)). If a participant experiences a grade ≥ 3 toxicity or an intolerable adverse reaction, dosing should be withheld for one week or until symptoms improve to grade ≤ 2 , then resumed at the same or a reduced dose (120 mg or 80 mg) if warranted.

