6.6.3 Dose reduction

Darolutamide

If considered necessary for the participant's safety, the dose of darolutamide may be reduced to 300 mg bid. The medical monitor must be notified of any dose reduction.

Dosing of darolutamide below 300 mg bid is not allowed. If a grade 3 or higher treatment-related AE occurs while the participant is on 300 mg bid, the participant must be withdrawn from darolutamide.

When an AE leading to dose reduction improves or is resolved, dose re-escalation to 600 mg bid may be considered at the discretion of the investigator.

Enzalutamide

Dose reduction of enzalutamide can be done according to the prescription information ([XTANDI™ Prescribing information](#)). The medical monitor must be notified of any dose reduction.

When an AE leading to dose reduction improves or is resolved, dose re-escalation may be considered at the discretion of the investigator.

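### SAP 5.5.4 Percent Compliance uses the unmodified full dose as its denominator, so a fully adherent participant scores below 100% after a dose reduction or a resumed hold

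*SAP*

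**What the plan says.** SAP 5.5.4 builds the figure from three definitions. Exposure runs from first to last dose, counting both days. Actual dose is everything administered. For the denominator: "Total Intended Dose is defined as the sum of intended doses during the duration of exposure, based on no modifications to dose or schedule". The ratio of actual to intended, times 100, is Percent Compliance. It is summarised with descriptive statistics and in three categories: "The frequency and percentage of patients receiving <100%, 100%, and >100% of their dose compliance are summarized". A separate summary covers dose changes: "The number of patients with dose reductions, increased, interrupted and withdrawn (along with their reasons) are all summarized".

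The protocol uses a different reference. Section 6.4 assesses compliance by questioning participants and counting returned tablets or capsules, and adds: "Deviation(s) from the prescribed dosage regimen should be recorded in the source records and eCRF".

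Protocol 6.6.2 and 6.6.3 then change what is prescribed:

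- **Darolutamide.** A related grade 3 or 4 AE requires a hold until grade 2 or less (Table 6–1 excepts clinically non-significant, asymptomatic laboratory abnormalities). After that, "Darolutamide treatment is then to be restarted at 300 mg bid". Once the AE improves, "dose re-escalation to 600 mg bid may be considered at the discretion of the investigator".
- **Enzalutamide.** For a grade 3 or higher toxicity or an intolerable reaction, dosing is withheld for a week or until improvement, "then resumed at the same or a reduced dose (120 mg or 80 mg) if warranted". Re-escalation is again left to the investigator.

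**The concern.** Compliance normally asks whether the participant took what he was told to take. The SAP ratio asks how much of the planned full dose was delivered, which is usually called relative dose intensity (a term neither document uses). The two agree only while the prescribed dose equals the full dose.

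After a protocol-directed reduction, or a directed hold with dosing resumed, they part. A participant who follows every instruction is then tabulated with those who skipped doses. The dose-change counts do not repair this, because they carry neither the duration of the change nor the dose taken during it, and are not linked to the ratio.

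What is at stake is interpretation. The one planned compliance figure could be read as non-adherence when it reflects toxicity management. If the randomized phase runs, a difference between arms could be misread in the same way, in an open-label comparison of tolerability-related outcomes.

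**Working it through.** The documents state no compliance result, so there is no figure to reproduce. The check applies the SAP formula to hypothetical participants who take every prescribed dose.

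**Inputs from the documents.** Full daily dose F: darolutamide 1200 mg, enzalutamide 160 mg (Protocol 1.1). Reduced daily dose D: darolutamide 600 mg (300 mg bid); enzalutamide 120 or 80 mg (Protocol 6.6.2).

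**Assumptions.** Exposure T = 364 days (52 weeks) or 168 days (24 weeks); one event at the end of week w; a 7-day hold; R days at the reduced dose, then full dose.

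**Formula.** Score = 100 × [7w·F + R·D + (T − 7w − 7 − R)·F] / (T·F). If the dose is never re-escalated, R = T − 7w − 7.

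**Step 1. Darolutamide, T = 364, denominator 364 × 1200 = 436,800 mg.**

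- Week 12, never re-escalated: 84 × 1200 + 273 × 600 = 264,600; score 60.6%.
- The same with the event at week 4: 231,000, or 52.9%. At week 38: 373,800, or 85.6%.
- Week 12, re-escalated after 28 days: 411,600, or 94.2%. After 7 days: 424,200, or 97.1%.

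**Step 2. Darolutamide, T = 168, denominator 201,600 mg, week 12 event.** Never re-escalated: 147,000, or 72.9%. Re-escalated after 28 days: 176,400, or 87.5%.

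**Step 3. Enzalutamide, T = 364, denominator 58,240 mg, week 12 event, no re-escalation.** Resumed at 160 mg: 57,120, or 98.1%. At 120 mg: 46,200, or 79.3%. At 80 mg: 35,280, or 60.6%.

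**Step 4. Non-adherent participants with the same scores.** A participant on full dose throughout who skips 39.4% of his tablets scores 100 − 39.4 = 60.6%, matching the first case in Step 1. One who skips 7 days on his own scores 357/364 = 98.1%, matching an instructed 7-day hold with full dose resumed.

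**Step 5. Where the effect stops.** If a participant takes full dose for 56 days, is put on hold and never restarts, exposure ends at day 56. The score is 67,200/67,200 = 100%.

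**Step 6. Between arms.** Take the 52-week scores for the same week 12 event.

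- Darolutamide never re-escalated, enzalutamide resumed at 160 mg: enzalutamide minus darolutamide is 98.1 − 60.6 = +37.5 points per affected participant.
- Darolutamide re-escalated after 28 days, enzalutamide kept at 80 mg: 60.58 − 94.23 = −33.7 points.

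If 5% to 15% of each arm were affected (assumed, and equal in the two arms), the difference in mean score would be +1.9 to +5.6 points in the first case and −1.7 to −5.0 in the second. The documents do not say which practice will prevail or how often such events occur.

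**Step 7. Same participants, prescribed dose as denominator.** The first case in Step 1 becomes 264,600/264,600 = 100%. The participant who skipped 39.4% stays at 60.6%, and the one who skipped 7 days stays at 98.1%.

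**The case against.** The strongest reply is that this is mostly a matter of naming. The SAP says openly that the denominator ignores modifications, so a careful reader knows what the ratio is. Protocol 6.4 defines no ratio, and reading its prescribed regimen as the dose prescribed at the time is an inference, though a natural one.

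Patient-level information is also planned. SAP 5.1 lists all raw data, the schedule footnotes require reasons for non-compliance to be recorded, and dose changes are tabulated with reasons. Compliance is not an endpoint, and no population, test or sensitivity analysis uses it. The lead-in has one arm, and its output index (SAP 9.0) shows no compliance table, although SAP 5.1 applies the analyses to both phases unless stated otherwise.

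Most of this stands as a limit on importance. It does not remove the defect: listings and counts are not a summary of adherence, and the plan contains no such summary.

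A reader might infer three stronger things that the documents do not support:

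- That every hold lowers the score. It does not when dosing never resumes (Step 5).
- That the measure favours one arm. The reduction on restart after a related grade 3 or 4 AE is required for darolutamide and optional for enzalutamide, but re-escalation is discretionary in both and no event rates are given, so the sign is open (Step 6).
- That adherence cannot be recovered at all. Individual cases might be pieced together from the listings.

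**Conclusion.** The point holds within these limits. As defined, Percent Compliance falls below 100% for a fully adherent participant in either arm after any reduction, or after an instructed hold followed by resumed dosing. The three-row table then cannot tell him from a participant who skipped doses.

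The size for one participant depends on the assumed course. At 52 weeks, with darolutamide kept at 300 mg bid after a 7-day hold, the score is 60.6% for a week 12 event and 52.9% to 85.6% for events at weeks 4 to 38. Prompt re-escalation brings it to 94.2% or 97.1%.

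No size or direction can be given for a difference between arms, and the question arises only if the conditional randomized phase goes ahead. The summary is descriptive and the primary TUG analysis does not depend on it. This is a worthwhile clarification, not a threat to the trial's conclusions.

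**What to change.** In SAP 5.5.4:

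1. Keep the present ratio and label it relative dose intensity (percent of planned dose).
2. Define Percent Compliance as dose taken divided by dose prescribed at the time, times 100. The denominator follows recorded reductions and re-escalations and leaves out instructed interruption days, by the same rule in both arms.
3. Use this second ratio for the <100%, 100% and >100% table.

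The cost is a small text change and one extra derived variable. Much of the data should already exist, since Protocol 6.6.2 says: "All dose modifications regardless of relatedness should be recorded on the CRF". The annotated CRF is not among the documents, so the sponsor must confirm that dose-change entries carry dates, and reasons that separate instructed holds from missed doses. If they do not, the derivation needs more than this.

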#### 5.5.5 Adverse Events

A TEAE is defined as any event arising or worsening after first dose study drug until 30 days after last dose. If an AE occurs before the first dose of treatment it will be considered a non-treatment emergent AE.

TEAEs and AEs will be summarized by frequency and percentage of patients and tabulated by MedDRA system organ class (SOC) and preferred term (PT), by maximum NCI-CTCAE version 5.0 grade and by drug relationship as not related and related to treatment. SAEs, TEAEs leading to treatment discontinuation and deaths will be summarized. Drug-related TEAEs by CTCAE grade, and drug-related grade 3 or higher TEAEs are summarized. Patients with multiple TEAEs or AEs are counted once within a summary category-SOC, PT, maximum grade, or relationship to treatments.

AESI be summarized by SOC and PT and grade in separate summary tables. All AEs will be listed.

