- the proportion of participants with a decline in cognitive function during the 24-week period from baseline, as assessed by HVLT-R and TMT

The suggested sample size for the randomized phase is based on the assessment of TUG test as the primary endpoint; however, after the feasibility assessment, the appropriate endpoint and the time point and time frame of evaluation of the endpoint for this part of the study will be chosen and the sample size will be reassessed.

The study is designed to evaluate physical function, including balance and daily activity, in participants treated with darolutamide or enzalutamide. It will also evaluate, safety, cognitive function, fatigue, and survival in participants treated with darolutamide or enzalutamide.

Participants will receive treatment (darolutamide or enzalutamide) until toxicity or disease progression and receive assessments during treatment. The study will continue until at least 52 weeks after the initial dose of the last participant, unless the participant discontinued due to lost to follow-up, withdrawal, or death. All participants will be followed up for survival status until the end of the study unless participants withdraw their informed consent.

The primary analysis for the lead-in phase will be performed when the last participant in the lead-in phase has been on the study for at least 24 weeks, unless the participant discontinued due to lost to follow-up, withdrawal, or death.

The primary analysis for the randomized phase for the study will occur when last participant in the randomized phase of the study has been on the study for at least 24 weeks, unless the participant discontinued due to lost to follow-up, withdrawal, or death. A final analysis for the randomized phase for the study will occur when last participant in the randomized phase of the study has been on the study for at least 52 weeks, unless the participant discontinued due to lost to follow-up, withdrawal, or death.

No data monitoring committee, dose escalation committee, or similar review group will be used for this study. The study will be conducted only in the USA at approximately 20 sites.

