	
  
 Test	Reliable Change Index threshold (from baseline)	
   
 Hopkins Verbal Learning Test - Revised Total Recall (HVLTR TR)	±5 words	
 
 Hopkins Verbal Learning Test - Revised Delayed Recall (HVLTR DR)	±3 words	
 
 Hopkins Verbal Learning Test - Revised Delayed Recognition (HVLTR RECOG)	±2 words	
 
 Trail Making Test: Part A (TMTA)	±12 seconds	
 
 Trail Making Test: Part B (TMTB)	±26 seconds	
 
 Controlled Oral Word Association (COWA)	±12 words	
  
 
 • The proportion of participants with a decline of >10 points from baseline in the FACT-Cog domain by 24 and 52 weeks will be summarized. 
Fatigue
 
 • The proportion of participants with an increase of at least 1 point in worst level of fatigue from baseline during the past 24 hours (item 3 of BFI) by 24 and 52 weeks will be summarized. • Similarly, the proportion of participants with an increase of at least 1 point in in fatigue interference from baseline during the past 24 hours (items 4A through F of BFI) by 24 and 52 weeks will be summarized. The proportion of participants with a decline and the 95% CIs will be summarized for each treatment arm. This rate will be compared between the two arms using Cochran-Mantel-Haenszel test adjusting for stratification factors as captured by IWRS. 
Depression
 
 • The proportion of participants with a worsening of scores by PHQ-9 during the 24 and 52 week period from baseline will be summarized. Worsening is defined as an increase of at least 1 point in worst level of depression from baseline by 24 weeks and 52 weeks. 
AE, Exposure, other
 
 • AEs, drug-related AEs, and SAEs will be summarized by MedDRA coding system and NCI-CTCAE version 5.0 worst grade. • AE of interest (fall, fracture, hypothyroidism) will be summarized descriptively. • Time to deterioration of KPS will be calculated as the time from randomization (or time from first dose for participants in the lead-in phase) to the first date the participant had a decline in KPS score of at least 10 points. Data will be summarized using the Kaplan-Meier method. • Treatment exposure of the study intervention, including time on treatment and dose reductions, will be summarized. 		Test	Reliable Change Index threshold (from baseline)	Hopkins Verbal Learning Test - Revised Total Recall (HVLTR TR)	±5 words	Hopkins Verbal Learning Test - Revised Delayed Recall (HVLTR DR)	±3 words	Hopkins Verbal Learning Test - Revised Delayed Recognition (HVLTR RECOG)	±2 words	Trail Making Test: Part A (TMTA)	±12 seconds	Trail Making Test: Part B (TMTB)	±26 seconds	Controlled Oral Word Association (COWA)	±12 words

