## 5.5 Safety and Tolerability Analysis

Safety analyses are based on the Safety population. Descriptive statistics are used to summarize the safety parameters. Safety data including AEs, AESI, laboratory parameters, vital signs, exposure and KPS. The protocol schedule of events and windowing will be used for the applicable safety table assessments.

Endpoints measuring physical function, daily activity and cognitive function will also be performed on the Safety population.

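### Randomized phase: falls, fractures and other AEs of interest are summarised only as crude percentages, so arms with different treatment lengths could show different percentages at the same true rate

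*SAP*

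**What the plan says.** Evaluating safety, AEs of interest included, for darolutamide versus enzalutamide is a secondary objective (Protocol section 3; SAP Table 1). Protocol 4.1 has participants treated "until toxicity or disease progression and receive assessments during treatment". The footnotes to the schedules of activities let treatment continue past Week 52, up to the final evaluation of the randomized phase.

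SAP 5.5.5 sets the treatment-emergent window: "A TEAE is defined as any event arising or worsening after first dose study drug until 30 days after last dose". The summary measure is a percentage of patients, counted once within each category: "TEAEs and AEs will be summarized by frequency and percentage of patients and tabulated by MedDRA system organ class". For AEs of special interest, "AESI be summarized by SOC and PT and grade in separate summary tables". SAP 5.5.3 likewise gives AEs as number and percentage of patients and AEs of interest descriptively. Protocol 9.4.2 agrees: "AE of interest (fall, fracture, hypothyroidism) will be summarized descriptively".

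Exposure is derived in SAP 5.5.4, "Duration of Exposure is defined as the duration between the first and last dose of treatment", but only for its own summary; it is never a denominator for AEs.

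Two provisions widen collection beyond the 30-day window. Protocol 8.3.1 collects SAEs to 30 days after the last dose but all AEs until the follow-up visit(s). Protocol 7.1 keeps participants who stop treatment in the study for evaluation to 52 weeks.

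**The concern.** A crude percentage mixes how often events occur with how long people were watched. When the window is tied to treatment length, two arms with the same underlying rate of falls give different percentages if one is treated longer. Darolutamide is studied here because it is expected to be better tolerated, and Protocol 2.2 names falls and fractures among the features that separate it from enzalutamide. If better tolerability led to longer treatment, the crude tables would count against the better-tolerated drug; if progression drove the difference, the distortion could go the other way. Counting each patient once also hides repeated falls.

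The same SAP handles unequal follow-up with Kaplan-Meier methods for TUG worsening, PSA progression and KPS deterioration. Falls and fractures receive no comparable treatment.

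At stake is the reading of a descriptive safety comparison. The primary TUG analysis is not affected.

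**Working it through.** **What the plan supplies.** There is no planned AE figure to reproduce: the documents give no fall, fracture or hypothyroidism rate for this trial and no expected treatment duration by arm. The sample-size statement fixes the arm size: about 120 randomized 1:1, so about 60 per arm. With 10% drop-out, 54 per arm gives 84.4% power (pooled variance) or 85.1% (unpooled) for 20% versus 40% at one-sided 10%, against 85% stated, so that figure reproduces.

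**Inputs.**
- From SAP 5.5.5: window = treatment time + 30 days; each patient counted once.
- Assumed: a constant event rate, identical in both arms; everyone in an arm treated for the same time, 12 months in one arm and 12, 10 or 9 in the other.

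**Formula.** Crude percentage = 1 − exp(−rate × window). The windows are 12/12 + 30/365.25 = 1.082 years, 10/12 + 0.082 = 0.915 years and 9/12 + 0.082 = 0.832 years.

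| Rate per year (assumed) | 12 months | 10 months | 9 months | Ratio 12 v 10 | Ratio 12 v 9 |
|---|---|---|---|---|---|
| 0.2 | 19.5% | 16.7% | 15.3% | 1.16 | 1.27 |
| 0.4 | 35.1% | 30.7% | 28.3% | 1.15 | 1.24 |

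With 12 months in both arms the ratio is 1.00.

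**Lower rates.** At 0.1 per year, 12 versus 9 months gives 10.3% versus 8.0%, ratio 1.28. In 60 per arm that is 6.2 versus 4.8 participants. At 0.05 per year it is 5.3% versus 4.1%, ratio 1.29. The ratio hardly depends on the rate; the absolute gap does.

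**Variable treatment length.** Suppose instead exponential discontinuation with median treatment of 24 versus 12 months (assumed) and rates of 0.05 to 0.2 per year. The crude ratio is 1.13 to 1.14 with a data cut at 12 months and 1.27 to 1.29 with a cut at 24 months.

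**Masking a real benefit.** With a true rate ratio of 0.7 favouring the longer-treated arm, and 0.1 per year in the other arm, the crude ratio is 0.71 at 12 versus 12 months and 0.91 at 12 versus 9 months. At 12 versus 6 months it reverses to 1.29.

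**Does a rate remove the artefact?** Under a constant rate, expected time at risk to first event is (crude percentage)/rate. At 0.2 per year this is 0.973 years for 12 months of treatment and 0.767 years for 9 months. Then 0.195/0.973 and 0.153/0.767 both return 0.20 per year, or 20 per 100 patient-years in each arm. Even a simpler denominator, not stopped at the first event, nearly does so. In the exponential example at 0.1 per year it gives 9.5 versus 9.6 per 100 patient-years at the 12-month cut and 9.2 versus 9.3 at the 24-month cut.

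**The case against.** **AE observation does not simply stop at 30 days.** A reader might infer that every participant is observed only until then. The documents do not support this. The limit applies to the TEAE definition and to SAE collection; Protocol 8.3.1 collects other AEs to the follow-up visit(s), and Protocol 7.1 keeps people who stop treatment in the study to 52 weeks. SAP 5.5.5 tabulates AEs as well as TEAEs and does not say which set the special-interest tables use. This objection stands. It also exposes a gap: the relevant time at risk cannot be settled until the AE set is named.

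**No direction can be asserted.** It is tempting to say that the longer-treated arm will look worse, or that this arm will be darolutamide. No durations by arm are given, treatment stops for progression as well as toxicity, and randomisation balances enrolment dates. Distortion requires discontinuation to differ between arms. This stands.

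**The tables are descriptive.** SAP 5.5 says "Descriptive statistics are used to summarize the safety parameters", and no between-arm AE test is planned. The lead-in has one arm, and the randomized phase is conditional on its findings. All true, but side-by-side columns under a darolutamide-versus-enzalutamide objective will be read as a comparison.

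**The gap is partly mitigated.** Duration of treatment is summarised and all AEs are listed, so an exposure imbalance would be visible. It would not be quantified for falls or fractures.

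**The assumed rates may be high.** Protocol 2.2 reports TEAE incidences below 10% in both arms of the earlier phase 3 trial of darolutamide, fatigue excepted. Lower rates leave the ratio almost unchanged but cut the gap to one or two people per arm. This limits the importance of the point and does not remove it.

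**Conclusion.** The point holds as a conditional weakness. The plan reports AEs of interest in the randomized phase as crude percentages, has a TEAE window that depends on treatment length, and uses no denominator in time. If discontinuation differs between arms, the percentages can differ at equal true rates: by a factor of about 1.15 to 1.16 for 12 versus 10 months and 1.24 to 1.27 for 12 versus 9 months, at an assumed 0.2 to 0.4 events per year with the 30-day tail. With equal durations there is no distortion.

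These figures rest on assumed rates and durations, a constant rate, and AE-of-interest tables restricted to TEAEs, which the SAP does not state. The documents do not show that a bias will occur or which arm it would favour. This is a cheap improvement to the safety reporting.

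**What to change.** In SAP 5.5.3 and 5.5.5, for the randomized phase only, keep the crude tables and add the following for falls, fractures and hypothyroidism:

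- **First-event incidence per 100 patient-years by arm.** Time at risk runs from first dose to the earliest of first event, last dose + 30 days, or the data cut. Give the rate ratio with 95% CI, labelled descriptive.
- **Fall events per patient-year by arm**, so that repeated falls are visible.
- **The AE set.** State that these tables use TEAEs, so that numerator and time at risk match.
- **One data cut for both arms.** Under Protocol 4.4.2, enzalutamide data stop at the final evaluation of the randomized phase while darolutamide participants may continue.
- **Hypothyroidism named explicitly.** It is an AE of interest in the protocol and in the SAP's own schedule footnotes, but is absent from the list in SAP 5.5.3.

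Limiting this to three events avoids rate ratios for all 16 categories in that list. The data are already planned, and neither conduct nor sample size changes. The cost is a few more tables, wide intervals with about 60 per arm, and a constant-rate assumption that should be stated beside the results.
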